Data collection for Aims 1 and 2. This RCT focuses on comparing NDPP outcomes between participants who receive Pre-NDPP vs. direct enrollment into the NDPP. The assessment schedule is shown in Table 1 below. Demographic characteristics will be extracted from EHR databases and verified as needed during the first study visit, including age, gender, race/ethnicity, preferred language, income (above/below 133% of federal poverty level), and education (highest level completed). Body weight will be measured on a high-capacity medical-quality scale at study visits and NDPP sessions. We will also provide study participants with a commercial-grade scale for in-home use (e.g., Inevifit's Premium Bathroom Scale I-BS002; https://www.inevifit.com/product/inevifit-premium-bathroom-scale-w-led-display-silver/) so that they can send us a picture of their weight via text message or email when not meeting in-person. The primary outcome is percent weight change from baseline to 12-months by ITT analysis (without regard to whether participants declined NDPP or had early dropout). We will also calculate percent weight change from the first to last NDPP sessions attended (i.e., last observation carried forward), per CDC guidelines.³⁷ CMS standards for NDPP reimbursement also emphasize achieving ≥5% weight loss at any point in the program, ¹⁰ assessed as a

dichotomous outcome. Attendance in the NDPP will be measured as ≥1 session attended, total number of NDPP sessions attended (including make-up sessions), and duration of participation in the yearlong program. We will also record how many sessions were attended remotely vs. in-person. Rates of completing between-session support calls will also be assessed as an additional indicator of engagement and treatment dose. Per the CDC's NDPP curriculum, participants will self-report weekly minutes of moderate to vigorous physical activity since the last session.³ Baseline BMI will also be assessed at the initial study visit as kg/m². If the initial study visit is held remotely (i.e., due to restrictions to meeting in-person per COVID-19), we will collect BMI by confirming height from a participant's medical record, and mailing a scale to participants for them to send us a picture of their weight within 1-2 weeks.

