We will measure Pre-NDPP costs using principles of time-driven activity based costing, ^{48,49} accounting for Lifestyle Coach and supervisor time (including salaries and benefits), supplies and other direct costs, and indirect costs (e.g., facilities and general administrative expenses). To focus on Pre-NDPP, we will exclude other costs associated with standard NDPP delivery and research-related costs (e.g., data collection solely for research purposes). To facilitate accurate estimates of personnel costs, coaches and their supervisor will track time spent on Pre-NDPP activities (e.g., training, outreach, preparing for and conducting Pre-NDPP) and report total hours for each Pre-NDPP activity quarterly. Supplies and other direct costs will also be reported quarterly. Standard cost collection guides will be used by study staff.

| Measure | easure Description Method of Collection | | | | | |
|--|--|--|---|--|--|--|
| Characteristics | | | | | | |
| Demographics | Age, gender, race/ethnicity, primary language, income, education, household composition, etc | Collected from EHR and during first study visit | BL | | | |
| Body mass index | Baseline body mass index (kg/m²) | Collected during first study visit (or within 1-2 weeks of remotely-conducted initial study visits) | | | | |
| | Main outcom | les | T | | | |
| Initial NDPP attendance | ≥1 NDPP session attended 1-25 NDPP sessions attended | Collected during NDPP delivery; | | | | |
| # of sessions attended | (including virtual vs. in-person sessions) | Note weight is also measured at an initial study assessment and at a final 12-month study visit | | | | |
| Duration in NDPP | 1-365 days of NDPP participation | (we are setting up a time for all randomized individuals to have | | | | |
| # of between-session calls completed | 1-25 between-session support calls completed | their weight measured at these study visits, for which they will | Ongoing collection | | | |
| Physical activity | Average self-reported weekly minutes at each NDPP session | receive gift cards). Participants may also text/email a picture of | | | | |
| Percent weight change | Based on a) BL to 12 months (primary outcome), and b) first to last NDPP sessions attended | their weight using a study- provided scale for in-home use if not meeting in-person for weight | | | | |
| ≥5% weight loss | Achieved at any point in the NDPP | collection. | | | | |
| | Mediators | | T | | | |

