| Maintenance (potential) – Extent to which intervention becomes routine practice and long-term participant benefits | Plans and intent to continue, or modify/adapt, Pre-NDPP after study; ROI as an indicator of potential sustainability; 12- month weight loss outcomes | QRA interviews with Lifestyle Coaches and select clinic staff; Document review and abstraction of NDPP payment schedules (e.g., Medicare); Above outcome data ive research assistant; ROI=return of | Study completion |

B. Description of Population to be Enrolled. As a pragmatic trial, we will recruit English- and Spanish-speaking adults who meet CDC-established NDPP eligibility criteria, including BMI≥25 (≥23 if Asian) and history of recent prediabetes or former GDM diagnosis.³⁷ Prediabetes is based on a laboratory test within the past year indicating a fasting blood glucose of 100-125, blood glucose of 140-199 measured 2 hours after a 75gm glucose load, or hemoglobin A1c of 5.7-6.4. GDM is based on past diagnosis in the medical record or self-reported. Patients without known prediabetes or past GDM may also be eligible based on a risk screening tool⁵⁰, as administered by Lifestyle Coaches during recruitment. Participants are excluded if pregnant at enrollment or known to have T2D.

C. Study Design and Research Methods.

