Description of the National Diabetes Prevention Program (for both conditions). The yearlong NDPP promotes modest weight loss through diet and physical activity. The curriculum is published by the CDC.3 We will follow CDC guidelines for implementing the standard group-based NDPP,³⁷ including 16 weekly to biweekly sessions, followed by ≥6 monthly sessions over a total of one year. The objective of NDPP is achieving ≥5% weight loss. Attending more sessions is associated with greater weight loss, 4,22 and guidelines allow NDPP sites to offer more than the minimum 22 sessions to support this goal. We will offer 25 total NDPP sessions (16 in months 1-6; 9 in months 7-12), held at the same time, day, and location in group visit rooms available at 8 neighborhood primary care clinics. There will also be an option to attend classes virtually via phone or videoconference. In light of COVID-19, in-person group classes will be offered when allowable by public health entities and Denver Health, although a virtual attendance option will remain for participants who prefer to join remotely. Two new NDPP classes will commence quarterly over 2.5 years. To minimize potential contamination, participants in the two study arms will be enrolled in separate NDPP classes. Trained, bilingual lay health educators will lead NDPP classes as Lifestyle Coaches and provide make-up sessions as needed. They will be observed by the research coordinator and/or qualitative research assistant for fidelity and to assess for potential bias in NDPP delivery. Weight is measured at each session on a high-capacity, medicalgrade scale, or by reporting their weight from a study-provided in-home scale. As required by the NDPP curriculum, participants are encouraged to achieve a weekly goal of ≥150 minutes of moderate to vigorous intensity physical activity (beginning gradually as needed). Participants are instructed to track start and stop times and report total weekly activity minutes at the following session. The most recent CDC curriculum also

encourages a low-fat diet, but does not require monitoring of dietary adherence.^{3,32} Lifestyle Coaches conduct support calls between sessions to support engagement and health behavior change, address individual questions and concerns, and remind participants about upcoming sessions.

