Coaches will then use MI techniques (e.g., reflective listening, evoking ambivalence, rolling with resistance, and eliciting change talk)²⁹ to help participants identify their preferred plan of action to reduce risk, encouraging participation in NDPP sessions. For example, to create discrepancy, coaches will acknowledge the difficulty of making changes in health behavior and probe for typical experiences of weight loss followed by weight regain or other similar challenges. To counter-balance these challenges, coaches will encourage participants to describe why preventing T2D is important to them (e.g., wanting to live a long and healthful life or setting a positive example for their children and grandchildren). Coaches will also non-judgmentally acknowledge that while the NDPP works well for those who attend regularly, it may be challenging for some individuals to attend a yearlong class, and that it is okay to opt out or choose other risk reduction resources.

Finally, to plan behavior to reduce diabetes risk, participants will be guided toward developing a personalized SMART (Specific, Measurable, Achievable, Realistic, and Time-bound) strategy for attending the NDPP. Coaches will help participants identify their anticipated barriers to attendance (e.g., need for childcare) and possible solutions that would enable participation (e.g., finding other caregivers or bringing children to class on occasion if needed). Participants will also be encouraged that more frequent attendance is associated with greater weight loss, but overall benefits can be achieved despite missing some sessions: attending ≥15 sessions is associated with achieving the ≥5% weight loss goal on average (i.e., each session is associated with 0.31% weight loss⁴). Scaling questions will be used to help individuals identify an appropriate initial goal. For example, although some participants may have limited confidence to make a commitment to attend the yearlong NDPP without having tried it before, they may report a 10 of 10 in confidence to attend at least the first NDPP session. Lastly, participants will complete an individualized action plan that includes their SMART goal and anticipated problem-solving strategies.

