D. Description, Risks, and Justification of Procedures and Data Collection Tools.

- 1) Pre-NDPP and NDPP classes
 - a. Description (see above description in section C)
 - b. Risks: Discussing diabetes risks may also be emotionally stressful. Muscle soreness or minor injury may occur from engaging in physical activity as recommended in the NDPP. To be safe, we encourage starting slowly with physical activity and checking with a doctor as needed. Participants may experience anxiety or distress related to answering personal questions or having weight collected. The National Diabetes Prevention Program classes are held in groups of other participants. We will ask the class to not share sensitive personal information outside of the group, but privacy cannot be guaranteed.
 - a. Why necessary: The one-time Pre-NDPP classes are being studied to see if they increase engagement in NDPP classes.
- 2) Study visits for survey completion and weight assessment
 - a. Description: Study visits will occur for 1) an initial eligibility and baseline assessment held in person (or remotely when needed due to restrictions on in-person meetings), 2) a follow up assessment in person, electronically, by mail, or by phone 1-2 weeks prior to the start of NDPP classes, and 3) a 12-month weight assessment in person (or collected remotely when needed).
 - b. Risks: Participants may experience anxiety or distress related to answering personal questions or having weight collected. The study investigators will make every effort to keep records private but it cannot be guaranteed.
 - c. Why necessary: Quantitative data collected from these visits will be used to answer research questions about the effectiveness of Pre-NDPP.

3) Interviews

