
Pre-NDPP cost and ROI. We will first calculate Pre-NDPP cost as the average expense of each presession delivery based on personnel time, supplies and other direct costs, and indirect costs. We will then determine the projected ROI of Pre-NDPP from both provider and payer perspectives. For NDPP providers, ROI will be calculated as the additional payment expected from payers as a result of potentially improved retention and weight loss of Pre-NDPP participants minus the average pre-session cost and divided by presession cost. For common reference, payments will be based on the Medicare reimbursement schedule for achievement of NDPP attendance and weight loss milestones. 10 We will compare the average expected reimbursement for participants in both study arms to measure additional payments that may be attributed to Pre-NDPP. We will also conduct a sensitivity analysis by calculating the projected ROI for varying numbers of Pre-NDPP participants with varying demographic characteristics (e.g., race/ethnicity, income), and with other available NDPP payment schedules (e.g., Maryland Medicaid⁶⁰). Sensitivity analysis results will inform Pre-NDPP sustainability by identifying the number of participants needed per pre-session to achieve a positive ROI, the extent to which moderators identified in Hypothesis 2.3 affect ROI, and the extent to which different payment models affect ROI. From the perspective of NDPP payers, ROI will account for the expected reduction in direct healthcare expenditures as a result of covering Pre-NDPP through an additional payment to NDPP providers, as calculated over a 3-year horizon. ROI will be the reduction in projected expenditures minus the average pre-session cost and divided by pre-session cost. Estimates of change in direct healthcare expenditures will be based on the impact of Pre-NDPP on weight loss from Hypothesis 1.1, the known relationship between weight loss and T2D incidence²⁰, and the difference in expenditures for individuals with prediabetes or T2D over a 3-year horizon.⁶¹ This timeline requires discounting of expected reductions in years 2 and 3 expenditures for which we will apply a standard 3% discount rate. We will also conduct a sensitivity analysis by varying the number of Pre-NDPP participants, their characteristics, and the discount rate. To be conservative, cost and ROI is based on all Pre-NDPP participants, regardless of NDPP attendance.

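### Payer ROI projects three years of savings from a 12-month weight difference without stating the weight path or varying it in the sensitivity analysis

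*Combined protocol and SAP*

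**What the plan says.** **Weight measurement.** Outcome Measures (IV.A): "The primary outcome is percent weight change from baseline to 12-months by ITT analysis". Table 1 adds: "Note weight is also measured at an initial study assessment and at a final 12-month study visit". The study visits listed in IV.D end with that visit. The program description in IV.C has 16 weekly to biweekly sessions "followed by ≥6 monthly sessions over a total of one year". No weight is scheduled after the program.

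**Payer ROI.** Under Aim 3 in the Data Analysis Plan (IV.F, Pre-NDPP cost and ROI): "Estimates of change in direct healthcare expenditures will be based on the impact of Pre-NDPP on weight loss from Hypothesis 1.1". Two further inputs are a literature relation between weight loss and type 2 diabetes incidence, and the difference in spending between prediabetes and diabetes. The horizon is three years, and reductions in years 2 and 3 are discounted at 3%. On sensitivity: "We will also conduct a sensitivity analysis by varying the number of Pre-NDPP participants, their characteristics, and the discount rate".

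**Maintenance.** Table 1 defines this RE-AIM construct as "Extent to which intervention becomes routine practice and long-term participant benefits". It measures it by plans and intent to continue, ROI, and 12-month weight loss. The row is labelled as potential.

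**Limitations.** Section IV.E admits reliance on literature estimates for cost savings and for the weight-incidence relation. It does not mention how long the weight difference lasts.

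**The concern.** Two of the three years in the payer projection come after the last weight, and in the first year the difference is still developing. The projection therefore needs an assumption about the between-arm difference at every point from 0 to 36 months. The trial supplies a 12-month value and, for those who attend, session weights before it. The plan does not say what is assumed for the rest.

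Followed as written, the analysis would give a payer ROI whose unobserved input is never varied, next to a discount-rate analysis that barely changes the answer. Aim 3 hypothesizes an ROI sufficient to justify the cost of pre-sessions, and the protocol looks to Medicare, commercial insurers and employers as possible supporters. Those readers would want to know how much of the projected saving depends on the path.

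Table 1 has a smaller version of the same problem. An end-of-program weight is listed as a measure of a construct that includes long-term benefit to participants.

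**Working it through.** The documents give no cost, savings or ROI figure, so there is nothing to reproduce. What can be checked is how sensitive the projected benefit is to the weight path.

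**Inputs from the protocol**
- Annual diabetes incidence 5.6% (Background, impaired fasting glucose).
- 16% lower incidence per kilogram lost (Background).
- 3% discounting from year 2 (IV.F).
- Pilot difference in weight loss: 3.4% - 1.5% = 1.9 percentage points (Preliminary Studies).

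**Assumptions not in the protocol**
- Body weight 90 kg, so the difference is 0.019 x 90 = 1.71 kg.
- Incidence follows current weight.
- A constant excess cost per diabetes-year, so that diabetes-years averted stand in for savings.

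**Formulas.** Let d(t) be the between-arm difference in kg at time t in years.
- Control hazard: 0.056.
- Intervention hazard: h(t) = 0.056 x 0.84^d(t). At the full 1.71 kg, 0.84^1.71 = 0.742, so h = 0.0416.
- Benefit: the integral over 0 to 3 years of [S1(t) - S0(t)] x 1.03^(-floor(t)), where S is diabetes-free survival in each arm.

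Each result is divided by the benefit with d(t) = 1.71 kg throughout. Regain is linear from month 12.

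| Path after month 12 | Full difference credited from time 0 | Difference builds linearly over year 1 |
|---|---|---|
| Held to month 36 | 1.000 | 0.707 |
| Half regained by month 36 | 0.935 | 0.643 |
| All regained by month 36 | 0.866 | 0.574 |
| All regained by month 24 | 0.755 | 0.464 |

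**Separating the two effects.** The year-1 build-up alone removes 1 - 0.707 = 29%. Regain alone removes 6.5%, 13% or 24.5%. Relative to build-up then held, regain leaves 0.643/0.707 = 91%, 0.574/0.707 = 81% or 0.464/0.707 = 66%. The year-1 path is thus the larger single influence.

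**Dependence on the size of the difference.** With 0.9 kg instead of 1.71 kg, the right-hand column becomes 0.701, 0.634, 0.564 and 0.455. The ratios hardly depend on the assumed body weight.

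**The planned financial sensitivity.** With a constant difference, a discount rate of 0% gives 1.043 and 5% gives 0.973, that is +4.3% and -2.7%.

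**Cross-check with a coarser model.** An annual-step cohort with full credit in year 1 gives 88% when the fractions in force are 1, 0.75 and 0.5, and 85% for 1, 0.75 and 0.25. These are close to the left-hand column. Abrupt loss of the whole difference at month 12, an extreme case, leaves 56% to 57%.

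**Break-even.** ROI = (B - C)/C, where B is benefit and C is cost. If a fraction f of the benefit is retained, ROI becomes (1 + ROI) x f - 1. It reaches zero at f = 1/(1 + ROI).

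**The case against.** **The plan does not say that the difference is constant.** This stands. A constant path is the natural reading, because the Hypothesis 1.1 effect is the only weight input and year 2 and 3 reductions are counted, but it is an inference. Starting the discount in year 2 is an ordinary convention and does not show that year 1 receives the full difference. The supportable criticism is that the path is unspecified and unvaried.

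**The cited weight-incidence relation may already reflect regain.** This also stands. If it links weight loss to incidence over several years, adding decay would count regain twice. The protocol gives no time basis for the 16% figure, so the model above is only an illustration.

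**A reader might infer that a positive payer ROI could come entirely from assumed persistence.** The documents do not support that. They give no cost or savings figure, and regain alone leaves 76% to 94% of the benefit. For regain alone to turn the sign, the constant-path ROI would have to be below 1/0.935 - 1 = 7%, 1/0.866 - 1 = 15% or 1/0.755 - 1 = 32%, depending on the case.

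**A reader might extend the point to all ROI and to Maintenance as a whole.** That goes too far. Provider ROI rests on payments for attendance and weight milestones and needs no persistence. Maintenance is labelled as potential and also uses plans and intent to continue. The 12-month weight change is already covered under Effectiveness, through the list of main outcomes.

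**Support for or against persistence elsewhere in the protocol is weak.** The Background mentions benefits lasting up to 15 years, but for the original trial, not for an increment from one pre-session. Conversely, the coaching prompt to "probe for typical experiences of weight loss followed by weight regain" is a motivational-interviewing device. It says nothing about the between-arm difference, which equal regain in kilograms in both arms would leave unchanged.

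**The plan has other safeguards.** It calls ROI projected, discloses its literature inputs and counts all Pre-NDPP participants regardless of attendance. Varying participant number can also matter more than the discount rate, because cost is per pre-session delivery. None of these varies the weight path.

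**Conclusion.** The point holds for payer ROI and for the participant-benefit part of Maintenance. The projection depends on an unstated weight path that the planned sensitivity analysis leaves untouched.

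In the illustration, the choice of path reduces the projected benefit by between 6% (regain alone, half by month 36) and 54% (year-1 build-up plus all regained by month 24). The discount-rate analysis moves it by about 4% or less. More of this comes from the year-1 path than from regain, so both need stating.

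The sizes rest on the assumed 90 kg, on incidence following current weight, and on savings being proportional to diabetes-years averted. Whether regain would reverse the sign of the payer ROI cannot be judged from the documents.

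This concerns the secondary economic aim. It does not affect the primary weight comparison or provider ROI. It is a cheap improvement to the plan, not a flaw in the trial.

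**What to change.** In the Pre-NDPP cost and ROI section of IV.F:

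1. State the weight path used for year 1, for example from the session weights already collected, or a linear build-up to month 12. Session weights exist only for attenders, so say how non-attenders are handled.
2. State whether the cited weight-incidence relation already reflects regain, and over what period it applies.
3. Add three cases for years 2 and 3 to the payer sensitivity analysis: difference held, half regained by month 36, and fully regained by month 36.
4. Report the break-even persistence, meaning the share of the 12-month difference that must last for payer ROI to reach zero. No pass/fail threshold is needed.

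In Table 1, describe the 12-month weight under Maintenance as an end-of-program outcome, not a long-term benefit.

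The cost is a few sentences of plan text and some extra model runs, with no new data. The downside is a wider and less favourable payer ROI.

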Aim 1: To evaluate clinical effectiveness of the Pre-NDPP intervention. We will recruit 500 diverse, predominately low-income patients with elevated diabetes risks (e.g., prediabetes) in the Denver Health safety net healthcare system. We will conduct a RCT to compare NDPP attendance and weight loss outcomes between participants randomized to receive the Pre-NDPP enhancement vs. direct enrollment into the NDPP (usual care). Pre-sessions, led by trained Lifestyle Coaches, will focus on providing information on diabetes risks and locally available resources to reduce risk, including the NDPP. Coaches will use MI techniques to help participants identify an actionable plan to reduce risk, such as attending NDPP sessions, and guide participants in identifying barriers and possible solutions that would enable participation. Pre-NDPP participants and usual care NDPP participants will be assigned to separate NDPP classes to prevent contamination of Pre-NDPP effects. We will collect data on demographics, NDPP outcomes (primary outcome is percent weight loss), potential mediators, implementation factors, and cost. We hypothesize that Pre-NDPP participants will have greater engagement and weight loss compared to those who are directly enrolled into the program (usual care).

Aim 2: To examine mediators and moderators of Pre-NDPP outcomes. We will explore potential mediators (perceived risk for developing diabetes and self-efficacy and readiness for weight control) and key sociodemographic variables (race/ethnicity and income level) as potential moderators of intervention effectiveness that are important to understand for future uptake by stakeholders. We hypothesize that a) Pre-NDPP will increase perceived risk, self-efficacy, and readiness, which will mediate relationships between presession treatment and NDPP outcomes, and that b) race/ethnicity and income level will moderate Pre-NDPP effectiveness.

Aim 3: To evaluate the implementation factors of Pre-NDPP. In preparation for potential future dissemination, we will evaluate implementation factors following a RE-AIM framework⁸, including a qualitative evaluation of pre-sessions from a Lifestyle Coach, clinic provider/personnel, and patient perspective. We will

also evaluate the cost of adding pre-sessions to NDPP delivery and projected return on investment (ROI). We hypothesize that Pre-NDPP will be implementable and yield sufficient projected ROI to justify its cost.

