Sample size and power. Pre-NDPP pilot data indicate a 0.36 effect size for percent weight change in the NDPP with an intraclass correlation coefficient (ICC) of 1.44%. To be conservative for our primary outcome of percent weight loss among all randomized participants regardless of NDPP participation, we estimate minimum effect sizes detectable for various sample sizes and ICCs (Table 2), with effect sizes of approximately 0.28 to 0.35 for analyses of the primary outcome with a type-1 error rate of .05. Consequently, we expect that 500 randomized participants will provide adequate power while accounting for expected attrition. Note that mediation and moderation analyses are considered exploratory, as estimated power is unknown.

| Table 2: Estimated power to detect treatment differences in percent weight loss. | | | | | |
|--|-----------------------|-----|-----------------------|---|-------|
| Groups per arm | Patients per group | ICC | Effective sample size | Detectable difference (effect size) | Power |
| 10 | 18 (180 per arm) | 1% | 154 | .32 | 80% |
| 10 | 18 (180 per arm) | 2% | 134 | .35 | 82% |

| 10 | 20 (200 per arm) | 1% | 168 | .31 | 81% |
|----|------------------|----|-----|-----|-----|
| 10 | 20 (200 per arm) | 2% | 145 | .33 | 80% |
| 12 | 20 (240 per arm) | 1% | 201 | .28 | 80% |
| 12 | 20 (240 per arm) | 2% | 174 | .31 | 82% |

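### The Aim 3 ROI conclusion and the break-even group size have no planned uncertainty interval: the ROI sensitivity analyses carry neither the sampling error of the trial effects nor several fixed cost and literature inputs

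*Combined protocol and SAP*

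**What the plan says.** Section I, Aim 3 makes ROI part of a hypothesis. The investigators "hypothesize that Pre-NDPP will be implementable and yield sufficient projected ROI to justify its cost". No number defines sufficient. The only benchmark is a positive ROI, which appears in Section IV.F under Pre-NDPP cost and ROI, where the plan seeks the group size per pre-session that achieves it.

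The same part of Section IV.F gives the two calculations.

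- **Provider ROI:** "We will compare the average expected reimbursement for participants in both study arms to measure additional payments that may be attributed to Pre-NDPP". The sensitivity analyses vary participant numbers, demographic characteristics and payment schedule. They are also meant to show "the extent to which moderators identified in Hypothesis 2.3 affect ROI".
- **Payer ROI:** "Estimates of change in direct healthcare expenditures will be based on the impact of Pre-NDPP on weight loss from Hypothesis 1.1". That effect is combined with a literature relationship between weight loss and diabetes incidence and a literature difference in expenditure over three years. Then "ROI will be the reduction in projected expenditures minus the average pre-session cost and divided by pre-session cost". The sensitivity analysis is one sentence: "We will also conduct a sensitivity analysis by varying the number of Pre-NDPP participants, their characteristics, and the discount rate".

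Section IV.F, Sample size and power, states that "mediation and moderation analyses are considered exploratory, as estimated power is unknown". Section IV.E names reliance on literature-derived inputs as a limitation of the economic analysis and does not mention the sampling error of the trial's own effect. No section plans a confidence interval, bootstrap, probabilistic analysis or range of effect sizes for ROI.

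**The concern.** Both ROIs take a between-arm difference estimated from the trial as their main input. If that estimate goes in as a single number, the ROI comes out as a single number, and its sign may be due to chance. The test of Hypothesis 1.1 does not settle this. It asks whether the effect differs from zero, whereas a positive ROI requires the benefit to exceed the cost.

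Two Aim 3 outputs depend on it: the statement that projected ROI justifies the cost, and the break-even group size that suppliers and payers would use in planning. ROI by moderator is a third output, and it draws on contrasts that the plan itself calls exploratory.

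**Working it through.** **1. Reproduce the plan's precision.** Table 2 gives 10 classes of 20 per arm. Effective n per arm = 200 / (1 + 19 × ICC).

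- ICC 1%: 200 / 1.19 = 168.1 (stated 168). Power at 0.31 is 81.1% (stated 81%).
- ICC 2%: 200 / 1.38 = 144.9 (stated 145). Power at 0.33 is 80.2% (stated 80%).

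The other four rows also reproduce.

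**2. Interval for the effect.** SE = √(2 / effective n), in SD units; the 95% half-width is 1.96 × SE. At effective n 168, SE = √(2/168) = 0.109 and the half-width is 0.214. An observed 0.31 then has an interval of 0.10 to 0.52, which is 0.31 to 1.69 times the estimate.

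**3. Carry it into ROI.** With n participants per pre-session, benefit b per participant and cost C per pre-session, ROI = n·b/C − 1. Assume that b is proportional to the effect and C is fixed. The lower limit of ROI is above zero only if the point ROI exceeds d / (d − half-width) − 1.

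| Effective n per arm | Observed effect d | 95% interval | Point ROI needed for lower limit > 0 |
|---|---|---|---|
| 168 | 0.31 | 0.10 to 0.52 | 2.2 |
| 145 | 0.33 | 0.10 to 0.56 | 2.3 |
| 201 | 0.28 | 0.08 to 0.48 | 2.3 |
| 168 | 0.36 (pilot) | 0.15 to 0.57 | 1.5 |
| 145 | 0.36 (pilot) | 0.13 to 0.59 | 1.8 |

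In the first row, a point ROI of 0.5 has limits 1.5 × 0.31 − 1 and 1.5 × 1.69 − 1, or about −0.5 to 1.5.

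**4. Break-even group size.** This is C/b, which varies inversely with the effect. In the first row its 95% range is 1/1.69 to 1/0.31 of the point value, or about 0.6 to 3.2 times. A reported break-even of 5 would be compatible with about 3 to 16.

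**5. Check the proportionality assumption on the payer side.** Section II gives a 16% lower incidence per kilogram. The pilot means (3.4% vs 1.5%) and effect size 0.36 imply an SD of 1.9/0.36 = 5.28 percentage points. Assume a baseline weight of 90 kg and compounding per kilogram. Then 0.31 SD is 0.31 × 5.28% × 90 = 1.47 kg, and the incidence reduction is 1 − 0.84^1.47 = 22.6%. At the interval limits it is 7.7% and 35.2%. If savings follow incidence, the required point ROI is 1.9 to 2.0 for assumed weights of 80 to 100 kg, instead of 2.2. The illustration does not depend much on strict proportionality.

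**6. Small number of classes.** With 10 classes per arm and 18 degrees of freedom, the multiplier is 2.10 instead of 1.96. The half-width in the first row becomes 0.229, and the required point ROI is 0.31 / (0.31 − 0.229) − 1, or about 2.8.

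**7. Moderators.** Take 250 randomized per arm, the expected mix in Section IV.C, and no clustering or attrition. Half-width = 1.96 × √(2/n).

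- Hispanic (58.2%, 145.5 per arm): 0.23 SD.
- Low-income (61.4%, 153.5 per arm): 0.22 SD.
- Non-Hispanic black (19.5%, 48.75 per arm): 0.40 SD.

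The moderator contrast itself is less precise. Hispanic against non-Hispanic gives 1.96 × √(2/145.5 + 2/104.5) = 0.36 SD. Low against higher income gives 1.96 × √(2/153.5 + 2/96.5) = 0.36 SD.

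**8. What is varied and what is not.**

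| Input | Provider ROI | Payer ROI |
|---|---|---|
| Participant numbers and characteristics | varied | varied |
| Payment schedule | varied | not an input |
| Discount rate | not an input | varied |
| Sampling error of the trial effect | not carried | not carried |
| Pre-session unit cost | fixed | fixed |
| Weight loss to diabetes; expenditure difference | not an input | fixed |

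**The case against.** The strongest defence has four parts.

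- **Varying group size is informative.** Cost is counted per pre-session, so n and b enter ROI as a product, and changing n moves ROI just as changing the effect does. The break-even search already shows how near ROI is to zero. This stands: a reader might infer that the varied inputs are known or minor, and for group size that is wrong. What the search lacks is any measure of how likely each ROI is.
- **The plan hedges.** ROI is called projected, dissemination is conditional on effectiveness, moderation is labelled exploratory, and the literature inputs are named as a limitation. This stands as context and lowers the stakes. It does not supply an interval.
- **The magnitude is generic.** An interval of about 0.3 to 1.7 times the estimate arises for any estimate equal to an effect with 80% power, and at the pilot effect it narrows to 0.41 to 1.59 (effective n 168). It is worked in weight-change units, while provider ROI depends on attendance and weight milestones. This stands, so the figures illustrate payer ROI only.
- **The smallest subgroup is a selective example.** A reader might infer from the non-Hispanic black half-width of 0.40 SD that subgroup ROI will be mostly noise. Hypothesis 2.3 uses Hispanic ethnicity and low income as its examples. Their within-group half-widths of 0.22 to 0.23 SD are smaller than the 0.31 SD effect, although the contrasts between groups are wider. The documents also do not say that a subgroup-specific effect will be used for every characteristic varied.

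**Conclusion.** The concern holds as an omission from the planned ROI analysis. Followed as written, the plan produces an ROI conclusion and a break-even group size with no account of the sampling error in the trial effects, and with unit cost and the payer literature inputs held fixed. At the precision in Table 2 this could reverse the sign of payer ROI for point values up to about 2.2, or about 1.5 at the pilot effect. Those figures assume 200 per arm, ICC 1%, benefit proportional to effect and fixed cost.

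Three stronger readings are not supported. The plan does not vary everything except the treatment effect, since several other inputs are also fixed. The sign of ROI is not shown to be in doubt, because the documents give no cost or ROI and expect a low-resource intervention. The lack of a planned interval does not mean that none could be reported; that the effects enter as single numbers is read from the formulas. The primary weight analysis is unaffected. The change should be made because an Aim 3 conclusion depends on it.

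**What to change.** In Section IV.F, Pre-NDPP cost and ROI, add a probabilistic sensitivity analysis for both ROIs:

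1. Draw the trial effects (reimbursement difference for the provider, weight effect for the payer) from their class-clustered estimates and standard errors. A class-level bootstrap is an alternative, but state that it is imprecise with 10 to 12 classes per arm.
2. Also draw the pre-session unit cost and, for payer ROI, the weight-to-incidence relationship and the expenditure difference. Resampling trial data alone would give intervals that are too narrow. Where a source gives no measure of spread, use a stated range.
3. Report a 95% interval for each ROI and for the break-even group size, and the proportion of draws with ROI above zero, which is the plan's own benchmark. Report the share of draws in which no break-even size exists because the drawn benefit is not positive.
4. Base the Aim 3 ROI conclusion on these results.
5. Report ROI by Hypothesis 2.3 moderator with intervals and labelled exploratory, in line with the sample size section.

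The cost is some extra programming and a less definite ROI statement. No new trial data are needed.
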